## 2.3 Treatment Assignment and Blinding

The study is not blinded.

During the dose-escalation phase, each subject who meets the eligibility criteria will be assigned open-label IP(s). A subject is considered entered into the study when the investigator notifies the IXRS that the subject meets eligibility criteria and is enrolled into the study.

During the dose-expansion phase, subjects will be randomized 2:1 to either receive MEDI0680 in combination with durvalumab, or nivolumab monotherapy. Subjects are considered randomized into the study when the site confirms eligibility and enters the subject into the IXRS and are assigned unblinded IP(s).

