## 3.2 Analysis Populations

The analysis populations are defined in Table 3.1.

Table 3.1 Analysis Populations

| Population               | Description  |
|--------------------------|--|
| As-treated
Population | Includes all subjects who receive any durvalumab (MEDI4736) or MEDI0680 (AMP-514) or nivolumab will be included in the As-treated Population and subjects will be analyzed according to the treatment they actually received. The As-treated Population will be used to evaluate baseline characteristics as well as all endpoints for the safety and efficacy profiles. |

Table 3.1 Analysis Populations

| Population                          | Description  |  |  |  |  |
|-------------------------------------|--|--|--|--|--|
| Re-treated Population               | Includes all PD subjects who are re-administered durvalumab (MEDI4736) or MEDI0680 (AMP-514) for up to 12 months after the initial study treatment period. The Re-treated Population will be used to evaluate safety and efficacy endpoints for re-treated subjects.  The Re-Treated Population will be presented as separate summaries if enough subjects are included in the population.   |  |  |  |  |
| DLT Evaluable
Population         | Includes all subjects enrolled in the dose-escalation phase who receive at least 2 protocol-assigned doses of durvalumab (MEDI4736) and MEDI0680 (AMP-514) for MEDI0680 (AMP-514) every 2-week dosing schedule and complete the safety follow-up through the DLT evaluation period (until the planned administration of the third dose for MEDI0680 (AMP-514) every 2-week dosing schedule or experience a DLT during the DLT evaluation period. |  |  |  |  |
| Response
Evaluable
Population | Includes any subject included in the As-treated Population who has a baseline disease assessment (DA) and either has at least one post-baseline DA and/or discontinued treatment due to death or disease progression prior to a post-baseline DA.  |  |  |  |  |

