## 3.4 Efficacy Analyses

## 3.4.1 Efficacy Endpoints and Analyses

The efficacy endpoints include best overall response (BOR); objective response (OR); disease control (DC); time to response (TTR); duration of response (DR); progression-free survival (PFS); overall survival (OS); and change from baseline in target lesion sum of diameters. All efficacy analyses will be analyzed based on the As-treated Population. Additional summaries may be presented for the Re-treated and/or Response-evaluable Populations. Time to disease assessments (TDA) will also be summarized.

For the dose escalation phase, efficacy analyses will be based on both an application of Response Evaluation Criteria in Solid Tumors (RECIST) 1.1 to investigator assessed tumor measurements and an application of *modified* RECIST 1.1 to investigator assessed tumor measurements. For the latter, RECIST 1.1 has been modified to require confirmation of PD. A confirmed PD will be a PD confirmed by a consecutive repeat assessment no fewer than 4 weeks later. A PD that occurs without follow-up scans to provide confirmation or only non-evaluable follow-up scans will also be considered a confirmed PD. No such modification will be made in the dose expansion phase.

In the expansion phase, efficacy analyses will be based on an application of RECIST 1.1 to investigator assessed tumor measurements and may also be based on the Blinded Independent Central Review (BICR) if such data is collected.

Time-to-event data will be summarized using Kaplan-Meier estimates (median time and two-sided 95% CI for median time). An 80% CI for median time *may* also be included.

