#### 3.4.1.6 Progression-free Survival

Progression-free survival (PFS) is defined as the time from randomization (dose expansion) / the first dose of IP (dose escalation) until the first documentation of disease progression or death due to any cause, whichever occurs first, regardless of whether the subject receives subsequent anticancer therapy prior to progression. Subjects who have not progressed at the time of analysis will be censored at the time of the latest date of assessment from their last adequate progression free disease assessment. Censoring rules are presented in Table 3.2. PFS is defined in months as follows:

PFS (months) = (Date of PD/death or censoring – Date of randomization (dose expansion) / the first dose of IP (dose escalation) first dose of IP+1) / (365.25/12)

The median PFS and its 95% CI will be estimated using the Kaplan-Meier method. An 80% CI for median time *may* also be included.

For the expansion phase, the difference in PFS between treatment groups will be tested for significance with a logrank test. The hazard ratio for the two treatment groups with two-sided 95% CI will be estimated by a Cox proportional hazard model controlling for the prespecified stratification factors as explanatory variables in the model. The proportion of subjects progression free and alive at 6 months and associated 95% CI will be estimated using the Kaplan-Meier method.

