#### **CENSORING OF PFS**

Table 3.2 Summary of Censoring Guidelines for Efficacy Endpoints

| Situation   | Date of PD/Death or Censoring   | PFS Outcome                          |
|---|---|--------------------------------------|
| Documented Progressive Disease (PD)   | Date of earliest sign of PD   | Event                                |
| Death prior to second scheduled post-baseline disease assessment or after an adequate post-baseline disease assessment  | Date of death   | Event                                |
| No PD or death at time of analysis or lost to follow-up   | Date of last adequate progression-
free disease assessment   | Censored                             |
| Death or PD immediately after ≥ 2 consecutive missed or non-evaluable disease assessments   | Date of randomization (dose expansion) / the first dose of IP (dose escalation) or last progression-free disease assessment prior to missed or non-evaluable assessments, whichever occurred last | Censored                             |
| Initiation of subsequent anticancer treatment   | Date of last adequate progression-
free disease assessment prior to
initiation of subsequent anticancer
treatment  | Censored for
Sensitivity Analyses |
| No tumor assessment at baseline and no evidence of PD at first post-baseline disease assessment, OR  No tumor assessment post-first dose, and no death prior to second scheduled post-baseline disease assessment | Date of randomization (dose expansion) / the first dose of IP (dose escalation)   | Censored                             |

PD = progressive disease; PFS = progression-free survival

Subjects having missing lesion data at baseline or no disease assessments post-first dose will have PFS censored at the date of randomization (dose expansion) / the first dose of IP (dose

escalation) unless the subject dies prior to the second scheduled post-baseline disease assessment in which case the death date will qualify as a PFS event.

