#### 3.4.1.7 Overall Survival

Overall survival (OS) is defined as the time from randomization (dose expansion) / the first dose of IP (dose escalation) until death due to any cause. A subject alive at the end of study or lost to follow-up will be censored for OS at the last date when the subject was known to be alive. OS is defined in months as follows:

OS (months) = (Date of death or censoring – Date of randomization (dose expansion) / the first dose of IP (dose escalation) + 1) / (365.25/12).

The median OS and its 95% CI will be estimated using the Kaplan-Meier method. For the expansion phase, the difference in OS between treatment groups will be tested for significance with a logrank test. The hazard ratio for the two treatment groups with two-sided 95% CI will be estimated by a Cox proportional hazard model controlling for the prespecified stratification factors as explanatory variables in the model. The proportion of subjects alive at 12 months and associated 95% CI will be estimated using the Kaplan-Meier method.

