## 4 INTERIM ANALYSIS

Interim futility analyses for MEDI0680/durvalumab combination vs nivolumab will be performed in a continuous manner using Bayesian predictive probability. Bayesian predictive probability is used in the setting of single-arm trials with tumor response endpoints such as OR and allows for continuous assessments for early Go/NoGo decision making (Lee and Liu, 2008). A joint Bayesian predictive probability approach has been developed which allows for continuous assessments of the delta  $(\delta)$ , or difference, of the ORRs between MEDI0680/durvalumab combination and nivolumab.

The interim analyses will begin after 20 subjects in the MEDI0680/durvalumab combination have been randomized and have reached their second post-baseline disease assessment or have completed study, whichever occurs first. Subject accrual may be paused in both treatment groups for the first interim analyses; however, an accrual pause may not be necessary if existing data upon enrollment of 20 subjects in the MEDI0680/durvalumab combination suggest futility criteria have not been triggered as per the predefined futility stopping criteria defined below. If futility is not triggered, further enrollment will continue without pause and continuous monitoring for futility will commence after an additional 4 subjects reach their second post-baseline disease assessment or completes the study, whichever occurs first, until enrollment is complete.

Given the existing observed data during the continuous monitoring stage, the joint predictive probability is obtained by calculating the probability of reaching a NoGo decision should the treatment groups be enrolled and evaluated to the maximum planned final sample size of 60 (40 in MEDI0680/durvalumab combination and 20 in nivolumab). Further enrollment into both treatment groups will be terminated due to futility if there is a high probability of reaching a NoGo decision upon enrollment of 60 subjects given the existing observed data (ie, predictive probability of a NoGo decision > 90%). An efficacy decision would be

reached if there is a high probability of reaching a Go decision upon enrollment of 60 subjects given the existing observed data (ie, predictive probability of a Go decision > 90%). If an efficacy decision is reached, enrollment may continue, but planning activities for further development of the MEDI0680/durvalumab combination may be triggered.

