Upon enrollment of 60 subjects in the dose-expansion phase, a final analysis will be performed. NoGo criteria will be met if the probability that the  $\delta$  exceeds the pre-specified

[figure not shown]
target of 20% is less than 10% (ie, NoGo:  $P[\delta > Target] < 10\%$ ). Go criteria will be met if the probability that the  $\delta$  exceeds the pre-specified target of 20% is more than 70% (ie, Go:  $P[\delta > Target] > 70\%$ ). For futility analyses, a response is defined as either a confirmed or unconfirmed CR or PR as per RECIST 1.1 and for the final analysis a response is defined as a confirmed CR or PR as per RECIST 1.1.

At interim analyses, efficacy and selected safety data will be summarized to assess the overall benefit-risk profile. The analysis populations to be used for the interim analysis are described below:

- As-treated with 17 weeks of potential follow up is defined as all subjects in the Astreated Population who have a baseline disease assessment and have an opportunity to be followed for at least 17 weeks (i.e., received the first dose of MEDI0680, durvalumab or nivolumab, whichever earliest, at least 17 weeks ago). The 17 weeks are to have at least 2 post-baseline disease assessments plus the one week visit window. This is the primary analysis population for the interim analysis of efficacy data.
- Response evaluable with 17 weeks of potential follow up is defined as all subjects in the As-treated Population who 1) have a baseline disease assessment; 2) have an opportunity to be followed for at least 17 weeks; and 3) have any post-baseline disease assessments or experience clinical PD/death. This is the secondary analysis population for the interim analysis of efficacy data.
- As-treated with 9 weeks of potential follow up is defined as all subjects in the Astreated Population who have a baseline disease assessment and have had an opportunity to be followed for at least 9 weeks. The 9 weeks are to have at least 1 post-baseline disease assessments plus one week visit window. This is the exploratory analysis population for the interim analysis of efficacy data.
- **As-treated Population**, as defined in section 3.2, is the primary analysis population for the interim analysis of safety data.

Figure 4-1 Decision Matrices for Continuous Monitoring

(MEDI0680 + Durvlumab vs Nivolumab: 10% false negative if effect = 20%)

[figure not shown]
[figure not shown]

Figure 4-2 Visual Joint Predictive Probability Operating Characteristics

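### The randomized expansion comparison has no all-randomized analysis set: efficacy is analysed only in dosed subjects, grouped by the drug received

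*SAP*

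**What the plan says.** Table 3.1 (Section 3.2) defines four sets: As-treated, Re-treated, DLT Evaluable and Response Evaluable. Entry to As-treated requires at least one dose of a study drug, and "subjects will be analyzed according to the treatment they actually received". Section 3.4.1 then applies it without distinguishing the phases: "All efficacy analyses will be analyzed based on the As-treated Population". Section 3.1 makes the same set the default. The optional additional efficacy sets, Re-treated and Response Evaluable, also contain only dosed subjects.

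The expansion phase is described as a randomized comparison. Section 2.2 gives a 2:1 allocation stratified by MSKCC risk group and PD-L1 status. Section 2.3 says the study is not blinded and that a subject counts as randomized once the site confirms eligibility and makes the IXRS entry. Sections 3.4.1.2, 3.4.1.3, 3.4.1.6 and 3.4.1.7 specify between-arm tests of ORR, DCR8 and DCR24, PFS and OS. PFS and OS in expansion run from randomization.

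Section 4 starts the interim analyses by a count of randomized subjects: "The interim analyses will begin after 20 subjects in the MEDI0680/durvalumab combination have been randomized" and have reached the second post-baseline assessment or completed the study. Its primary interim efficacy set requires that a subject "received the first dose of MEDI0680, durvalumab or nivolumab, whichever earliest, at least 17 weeks ago".

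**The concern.** Between an open assignment and the first dose, a subject can withdraw, deteriorate or die. Those losses can differ by arm and be related to prognosis. Restricting the comparison to dosed subjects, and regrouping them by drug received, gives up the protection of randomization exactly where the SAP makes a comparative claim.

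The SAP is also mismatched internally:

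- Follow-up for PFS and OS starts at randomization, but a death before the first dose can never be counted.
- The sample size counts 40 + 20 randomized subjects; the analysis counts dosed subjects.
- A subject dosed once and never scanned is a non-responder under Section 3.4.1.2, while a subject never dosed is in neither numerator nor denominator.

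The direction of any bias depends on which arm loses subjects. Dropping combination non-responders favors Go; dropping nivolumab non-responders works against it.

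**Working it through.** **1. The SAP's power figure, which assumes all randomized subjects are analysed.** Inputs from Section 2.4: 20 nivolumab at 21.5%, 40 combination at 47.5%, one-sided 0.10.

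- Pooled rate = (20 × 0.215 + 40 × 0.475)/60 = 0.3883
- Null SE = √[0.3883 × 0.6117 × (1/20 + 1/40)] = 0.1335
- Alternative SE = √[0.215 × 0.785/20 + 0.475 × 0.525/40] = 0.1211
- Power = Φ[(0.26 − 1.2816 × 0.1335)/0.1211] = 76.9%, against the stated 76%

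The figure reproduces, so the problem is the analysis set and not the power.

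**2. How far the two sets can diverge in expectation.** Hold ORR in dosed subjects at the planning values and count undosed subjects as non-responders. The As-treated difference stays at 26.0 points. The all-randomized difference becomes:

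- one undosed combination subject: 0.475 × 39/40 − 0.215 = 24.8 points
- one undosed nivolumab subject: 0.475 − 0.215 × 19/20 = 27.1 points

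**3. Effect on the final decision.** Section 4 gives Go if P(δ > 20%) > 70%, NoGo if < 10%, and otherwise Consider. The SAP text states no prior, so independent Beta(a, a) priors are assumed with a = 1 and a = 0.5. The posterior in each arm is Beta(a + r, a + n − r). With kc and kn undosed subjects (combination, nivolumab), responders follow Bin(40 − kc, 0.45) and Bin(20 − kn, 0.25), that is, Section 4's benchmark of 25% and true δ of 20%. As-treated uses denominators 40 − kc and 20 − kn; all-randomized uses 40 and 20. The table sums the probability of outcomes whose category differs.

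| Undosed (assumed) | Beta(1,1) | Beta(0.5,0.5) |
|---|---|---|
| none | 0 | 0 |
| 1 combination | 8.0% | 0.4% |
| 2 combination | 9.7% | 10.0% |
| 1 nivolumab | 3.0% | 9.5% |
| 2 nivolumab | 10.8% | 12.5% |
| 1 in each arm | 1.1% | 3.0% |
| 2 combination + 1 nivolumab | 8.3% | 0.1% |

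Every change is to or from Consider; the probability of a Go/NoGo reversal is zero in all rows.

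Calibration: with nobody undosed, this model gives Go/NoGo rates of 24.5%/11.6% for Beta(1,1) and 31.4%/10.4% for Beta(0.5,0.5). Table 4.1 shows 28%/7% at δ = 20%. Neither prior reproduces the SAP's own row, so the table above is illustrative.

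**4. Single outcomes near a threshold.**

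- 19/40 vs 4/20 gives P(δ > 20%) = 0.674 under Beta(1,1), Consider. Dropping one undosed combination non-responder (19/39) gives 0.707, Go. Under Beta(0.5,0.5) the values are 0.710 and 0.741, both Go.
- 17/40 vs 5/20 has one-sided Pearson p = 0.092; with 5/19 it is 0.115.
- 16/40 vs 5/20 has p = 0.125; with 16/38 it is 0.099.
- The last two pairs cross 0.10 in opposite directions. Fisher's test stays above 0.10 in all four cases (0.149, 0.181, 0.196, 0.159).

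**5. Time-to-event endpoints.** The text under Table 3.2 says: "Subjects having missing lesion data at baseline or no disease assessments post-first dose will have PFS censored at the date of randomization", unless death occurs before the second scheduled assessment. So for PFS an all-randomized set mainly adds early deaths, and never-dosed, unassessed survivors contribute almost nothing. For OS, both deaths and follow-up time would be added.

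**The case against.** The harm is conditional. This is a 60-subject Phase 1/2 study with an internal decision rule; As-treated is stated openly, and nothing in the SAP calls the expansion analysis intent-to-treat. If all subjects are dosed as assigned, the sets are identical. The numerical illustration rests on assumed undosed counts and on priors that do not reproduce Table 4.1. It is unstable (8.0% against 0.4% for the same single subject), and losses in both arms can partly cancel. The worked outcomes were chosen near thresholds.

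All of that stands as a limit on the size of the effect. It does not answer the structural point: As-treated suits the non-randomized escalation phase, but expansion carries significance tests, hazard ratios and a Go/NoGo rule on a randomized difference.

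Three supporting points are weaker. A timing trigger and an analysis set need not coincide, so the interim mismatch is not an error in itself. The Table 3.2 wording can be read as already covering a never-dosed subject once included, so changing it is clarification. Section 2.2 plans survival follow-up for all subjects but does not mention never-dosed ones; how they are followed is a protocol matter not shown here.

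**Conclusion.** The concern holds. The SAP fixes a dosed-only, by-drug-received set for every expansion efficacy comparison, and no section restores an all-randomized analysis. The missing-response rule in Section 3.4.1.2 works only inside As-treated, so it does not bring undosed subjects back.

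The size and direction of bias cannot be known from the document, and most results would not change. Under the stated assumptions (one or two undosed subjects in one arm, nivolumab ORR 25%, δ 20%, two candidate priors), the final category differs with probability between 0.4% and 12.5%. Subjects given the other arm's drug were not modelled. The case for change rests on the design mismatch and not on any one of these figures. It should be corrected, preferably before comparative results are known, so that the choice of set is not made after the fact.

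**What to change.** - Add an Intent-to-treat Population to Table 3.1: all subjects randomized in expansion, analysed by assigned arm.
- Make it primary for expansion ORR, DCR8/DCR24, PFS, OS and the final Go/NoGo assessment. Count undosed or unassessed subjects as non-responders for ORR.
- Base the interim 17-week and 9-week efficacy sets on randomized subjects by assigned arm, timed from randomization.
- In Table 3.2 and the text below it, refer to assessments after randomization for expansion, so that never-dosed subjects are plainly covered.
- Keep As-treated for safety, for escalation and as an efficacy sensitivity analysis.
- Report, by arm, the number randomized but not dosed and the number given the other arm's drug.

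The cost is SAP wording and one more analysis set. Assignments are already in the IXRS and the planned sample size is unchanged. ORR estimates would be slightly lower if anyone is undosed, and never-dosed survivors would add little PFS information. The sponsor should also confirm that never-dosed subjects are followed for survival.

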## 2.2.1 Treatment Regimen

Subjects will be treated in either the dose-escalation or dose-expansion phase. MEDI0680, durvalumab and nivolumab will be administered via IV infusion. In dose-escalation phase, subjects will remain on treatment for up to 12 months. In the dose-expansion phase, subjects will remain on treatment until unacceptable toxicity, confirmed PD, or development of other reason for treatment discontinuation.

In the dose-escalation phase only, subjects who achieve and maintain DC (ie, CR, PR, or stable disease [SD]) through the end of the 12-month treatment period will enter follow-up. During the first 12 months of follow-up, if the subject has PD, the subject may be re-administered MEDI0680 and durvalumab for up to another 12 months with the same treatment guidelines followed during the initial 12-month period if the subject fulfills the criteria for re-treatment in the setting of PD, has not received other anticancer treatments for their disease, and does not meet any of the IP discontinuation criteria as described in the protocol. Only 1 round of re-treatment will be allowed.

Nivolumab will be administered according to the package insert guidelines.

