#### 3.4.1.1 Best Overall Response

Best overall response (BOR) will be based on all post-baseline disease assessments that occur prior to the initiation of subsequent anticancer treatment. If re-treatment is permitted following an initial disease progression, a BOR will be reported separately for the re-treatment period. BOR will be summarized with the number and percentage of subjects for

the following categories: complete response (CR); partial response (PR); stable disease (SD); progressive disease (PD); and non-evaluable (NE).

At least 6 weeks from randomization (dose expansion) / the first dose of IP (dose escalation) first dose of IP must elapse without a radiological disease progression in order to assign a best overall response of SD. The definition of 6 weeks will allow for the protocol-defined disease assessment window of 3 days. Confirmation of PR and CR is required and must occur no fewer than 4 weeks after initial documentation of PR or CR. If a PR or CR that is pending confirmation is designated at an assessment followed by 1 or more non-evaluable assessments for CR or 1 or more non-evaluable assessments or assessments of SD for PR, response may be confirmed thereafter. Confirmation of PD is required in the dose escalation phase, but not the dose expansion phase. A confirmed PD will be a documented occurrence of a PD that is confirmed by a consecutive repeat assessment no fewer than 4 weeks later. A PD that occurs without follow-up scans to provide confirmation or only non-evaluable follow-up scans will also be considered a "confirmed" PD.

Concordance/discordance of disease assessment by investigator and derived disease assessment will be summarized in frequency table.

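### In dose escalation, a scan taken on a new anticancer drug can refute an earlier PD under modified RECIST 1.1, which lengthens PFS and DR and conflicts with BOR

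*SAP*

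**What the plan says.** Escalation efficacy is analysed in two ways. Section 3.4.1 states that "efficacy analyses will be based on both an application of Response Evaluation Criteria in Solid Tumors (RECIST) 1.1 to investigator assessed tumor measurements" and on a modified version that requires PD to be confirmed. For the modified version, "A confirmed PD will be a PD confirmed by a consecutive repeat assessment no fewer than 4 weeks later". There is a default: "A PD that occurs without follow-up scans to provide confirmation or only non-evaluable follow-up scans will also be considered a confirmed PD". Section 3.4.1.1 repeats both rules. Section 3.3.5.4 names modified RECIST 1.1 as the criterion for dating escalation endpoints.

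The endpoints treat later therapy differently:

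- **BOR (3.4.1.1):** "Best overall response (BOR) will be based on all post-baseline disease assessments that occur prior to the initiation of subsequent anticancer treatment". For re-treated subjects, "a BOR will be reported separately for the re-treatment period".
- **PFS (3.4.1.6):** measured to progression or death, "regardless of whether the subject receives subsequent anticancer therapy prior to progression". Table 3.2 and the text below it offer censoring at subsequent treatment only as an optional sensitivity analysis.
- **DR (3.4.1.5):** takes its end or censoring date from Table 3.2.
- **DCR8 and DCR24 (3.4.1.3):** need a BOR of CR, PR or SD. SD duration runs to first progression or death, with no cut at new therapy.
- **Locoregional therapy to target lesions (3.3.5.3):** a later response or SD is set to non-evaluable.

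**The concern.** A confirmation rule for PD is meant to separate true progression from a transient finding on the same treatment. That works only if the repeat scan is taken on that treatment. Here the repeat scan may be taken after a new systemic drug has started. If the new drug shrinks the tumour, the PD on study treatment is left unconfirmed and follow-up for PFS and DR continues.

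The subjects whose failure disappears are those who do well on the next therapy, so the error favours the study combination. Modified RECIST 1.1 is the criterion named in the escalation secondary objective (section 2.1.2), so these results should be right on their own terms. The SAP also becomes inconsistent within one subject, because BOR and PFS use different sets of scans to decide whether the same PD counts.

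**Working it through.** The SAP gives no figure to reproduce, so the check traces the rule through each endpoint and applies the SAP's own formula.

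**Inputs.** The PFS formula is (days + 1) / (365.25/12), and 365.25/12 = 30.4375 days per month (section 3.4.1.6). The scan interval is inferred as 8 weeks. Section 3.4.1.6 equates 17 weeks with two assessments plus one week, so (17 − 1)/2 = 8. Section 4 equates 9 weeks with one assessment plus one week, so 9 − 1 = 8.

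**Worked subject A.** SD at week 8, PD at week 16, new systemic drug at week 18, evaluable non-PD scan at week 24.

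- PFS if the week-16 PD counts: (112 + 1)/30.4375 = 3.71 months, event.
- PFS as written: the week-24 scan is the consecutive repeat assessment, at least 4 weeks later, and is not PD. There is no event at week 16. If censored at week 24, PFS is (168 + 1)/30.4375 = 5.55 months. If the next PD is at week 32 or 40, it is (224 + 1)/30.4375 = 7.39 or (280 + 1)/30.4375 = 9.23 months.
- DR in a responder with the same sequence is extended by at least one scan interval: 56/30.4375 = 1.84 months.
- DCR24: BOR is SD from week 8. If SD duration is ended using only scans in the BOR window, the week-16 PD has no follow-up scan, is confirmed by default, and DCR24 fails. If it is ended using the PFS scans, SD reaches 168 days, which is 24 weeks, and DCR24 succeeds. The SAP does not say which set applies.
- Optional sensitivity analysis: the subject is censored at the last progression-free scan before week 18. That is week 8, or week 16 if the unconfirmed PD visit is classed as progression-free. Either way the event is not restored.

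**Worked subject B.** PD at week 8, new drug, non-PD scan at week 16. For BOR the week-16 scan is excluded, the PD is confirmed by default, and BOR is PD. For PFS the week-16 scan is kept, so there is no event at (56 + 1)/30.4375 = 1.87 months. One subject under one set of criteria is both progressed and progression-free. ORR, DCR8 and DCR24 do not change, because BOR is PD.

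**Weight of one subject in DCR24.** 1/36 = 2.8 points if about 36 escalation subjects are pooled, and 1/6 = 16.7 to 1/3 = 33.3 points in a group of 6 or 3. This is what reclassifying any one subject does. It does not show how many are affected.

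**Illustration on assumed inputs, none from the SAP.** Progression times were simulated as exponential with 8-weekly scans, and a given share of PDs was cancelled, with the event delayed by 16 or 24 weeks. DCR24 uses the wider scan set. With a true median of 4 months:

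| PDs cancelled | 6-month PFS, 16-week delay | 6-month PFS, 24-week delay | DCR24 | DCR8 |
|---|---|---|---|---|
| 0% | 38.5% | 38.5% | about 53% | 72.7% |
| 10% | 41.9% | 44.6% | about 55% | 72.7% |
| 20% | 45.4% | 50.8% | about 57% | 72.7% |
| 30% | 48.7% | 56.9% | about 59% | 72.7% |

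With medians of 3 and 6 months and 20% cancelled, 6-month PFS rises by about 6 to 14 points and DCR24 by about 3 to 5. Median PFS moves in scan-interval steps and did not move at 10% cancelled or fewer.

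**The case against.** Several counter-arguments have force.

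- **The PFS wording is about therapy started before progression, and Table 3.2 makes documented PD an event at its earliest sign.** On this view the week-16 PD stands. But under modified RECIST 1.1 an unconfirmed PD is not yet a progression, and Table 3.2 only dates a PD that counts. No sentence in the SAP keeps the scan on the new drug out of the confirmation test.
- **The parallel unmodified RECIST 1.1 analysis keeps the first PD.** This is correct, and it is the main limit on the impact.
- **DCR24 is built on BOR, which is cut at subsequent treatment.** This stands in part. The DCR24 effect depends on an unstated choice, so it is possible, not established.
- **The number of affected subjects is unknown, and escalation has no between-arm test.** Both points stand. The expansion ORR comparison is untouched because PD confirmation does not apply there.

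A reader might also infer that re-treatment scans inflate disease control, or that re-treatment results are separated only for BOR. The document supports neither. Section 2.2.1 opens re-treatment only to subjects who kept disease control through the 12-month treatment period: "During the first 12 months of follow-up, if the subject has PD, the subject may be re-administered MEDI0680 and durvalumab", subject to further protocol criteria. Those subjects have already met DCR8 and DCR24. Table 3.1 defines a Re-treated Population ("Includes all PD subjects who are re-administered durvalumab (MEDI4736) or MEDI0680 (AMP-514) for up to 12 months after the initial study treatment period") for safety and efficacy endpoints, with separate summaries if numbers allow, and section 3.4.1 allows such summaries for efficacy. The protocol's re-treatment criteria are not at hand and may require confirmed PD first. For re-treatment, what remains is an unclosed gap in PFS and DR beyond 12 months, not a demonstrated bias.

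**Conclusion.** The point holds for PFS and DR in dose escalation under modified RECIST 1.1 after a new systemic therapy. The stated rule lets a scan on another drug cancel a PD on study treatment, and the same subject's BOR can still be PD. In worked subject A, PFS goes from 3.71 to at least 5.55 months. DCR24 may also be inflated, depending on which scans end SD duration. ORR is not affected, nor is DCR8 on an 8-week schedule. Locoregional therapy to target lesions cannot cause the problem, because section 3.3.5.3 makes a later response or SD non-evaluable.

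The conclusion rests on the inferred 8-week interval and on reading the confirmation rule as written. The cohort-level effect cannot be sized from the SAP, and the simulated figures show direction and plausible range only. Severity is minor: a secondary objective, no between-arm test, and an unmodified analysis alongside.

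**What to change.** Add to sections 3.4.1 and 3.4.1.1, for modified RECIST 1.1 PFS, DR and SD duration:

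1. Only assessments made before subsequent anticancer treatment, and before the first re-treatment dose, may confirm or refute a PD.
2. A PD with no evaluable assessment in that interval is a confirmed PD, dated at its first documentation.

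This extends the SAP's existing default for PDs without follow-up scans and its BOR cut to the other endpoints, so that BOR, PFS, DR and SD duration use the same scans to decide whether a PD counts. For re-treatment it only closes the gap described above.

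The cost is two sentences and one date condition in the derivation. No data collection or clinical management changes. Escalation PFS, DR and DCR24 may look slightly less favourable.
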